The Group Lifestyle Balance (GLB), derived from the Diabetes Prevention Program, is an established healthy lifestyle intervention that is efficacious in the general population for achieving clinically significant weight loss. Studies in the general population, including among racial/ethnic minorities, have shown that translating GLB to real-world settings is enhanced through the use of a group format and trained lay workers who deliver the intervention without compromising its effectiveness. Similar interventions that use GLB principles produce clinically significant weight loss among people with SMI, but their impact is limited as they tend to be delivered in clinical settings using healthcare professionals, making them prohibitive for community agencies. We aim to improve the reach of GLB in this study by: 1) bringing this intervention to people's doorsteps through its delivery in supportive housing agencies, and 2) using peer specialists (individuals with lived experience of SMI) as facilitators to address economic and staffing demands.

In this study, we aim to test the effectiveness of delivering a 12-month peer-led GLB (Peer GLB) intervention in supportive housing agencies. We will enroll up to 300 clients that are overweight or obese (BMI > 25) to participate in a randomized controlled effectiveness trial. Clients will be randomly assigned to either 1) the 12-month Peer GLB intervention (n=150) or 2) to usual care (n=150). GLB intervention fidelity will be monitored throughout the study through fidelity checklists, attendance logs, and trial records that capture participants' degree of completion of intervention activities. Outcomes will be evaluated through repeated assessments with participants via structured face-to-face interviews that will occur at baseline and 6, 12, and 18 months post-randomization. We will conduct 10 post- intervention focus groups with participants randomized to the Peer GLB group once they have completed the 12 month intervention to learn about their experiences with Peer GLB.

We have identified three supportive housing agencies that are participating in the project: [REDACTED] [REDACTED] houses clients in apartments throughout the community, offers a variety of health, mental health and social services and employs peer specialists. The site at [REDACTED] will be at [REDACTED]
[REDACTED]

The second site is [REDACTED] located at [REDACTED]
[REDACTED]

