The third site is [REDACTED] located at [REDACTED] [REDACTED] [REDACTED].

This study is part of a larger project that focuses on investigating the implementation and effectiveness of Peer GLB. The present protocol focuses on the effectiveness trial using the RCT study, which is represented by Aims 1-3 outlined in the grant proposal for the current NIMH funded study (1R01MH104574-01: see grant attached). A different IRB protocol for the mixed methods implementation study (Aim 4) was previously submitted and approved: IRB-AAAN5207. We will be submitting as a protocol modification all Spanish translation of study materials (e.g., consent forms, capacity-to-consent, structured interviews) once the English versions have been approved.

2. Study Design and Statistical Procedures

We will use a randomized controlled trial design in order to test the effectiveness of Peer GLB vs. usual care (UC) in supportive housing agencies. Peer GLB lasts 12 months and consists of weekly core group sessions (3 months.), bimonthly (twice a month) transitional group sessions (3 months.), and monthly maintenance sessions (6 months). Peer specialists in the housing agencies will be trained and supervised by the study team and the supportive housing agencies to deliver Peer GLB. Repeated participant assessments conducted by trained study staff (e.g., research assistants) will occur at baseline and at 6, 12, and 18 months post-randomization.

Primary Aim:

1. Compare the effectiveness of Peer GLB vs. UC in achieving clinically significant weight loss (5% weight loss) among overweight/obese (BMI 25) clients in supportive housing agencies.

Primary Hypothesis: Peer GLB participants will have a higher proportion of persons achieving

clinically significant weight loss (5% weight loss) at 12 and 18 months than UC participants.

Secondary Aims:

2. Compare secondary outcomes: reductions in total weight, waist circumference, blood pressure, and improvements in physical activity, self-efficacy, recovery, and quality of life at 6, 12, and 18 months between Peer GLB and UC. Secondary Hypothesis: At 6, 12, and 18 months post- randomization, there will be significant reductions in average weight, waist circumference, blood pressure, and significant improvements in physical activity, self-efficacy, recovery, and healthrelated quality of life in Peer GLB compared to UC.

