3. Explore whether client-level characteristics (e.g., socio-demographics, use of antipsychotic medications, attitudes toward Peer GLB) moderate Peer GLB's effectiveness.

We will use descriptive and multivariate statistics (e.g., logistic regression, generalized linear mixed effects models) to examine differences in primary and secondary outcomes between the Peer GLB intervention and UC groups. We will also explore interactions between treatment conditions and client- level characteristics (e.g., socio-demographics) to examine how these characteristics moderate Peer GLB's effectiveness.

3. Study Procedures

In this study, we will examine the effectiveness of Peer GLB among adult clients in supportive housing agencies who have SMI and are overweight or obese (BMI > 25), thus placing them at risk for cardiovascular disease. We will recruit clients through provider and self-referrals. We plan to recruit up to 300 clients to participate in this RCT. Eligible clients are: active supportive housing agency clients who are residing in supportive housing, are 18 years of age or older (18 to 90 years old), of any race/ethnicity, speak English or Spanish, have chart diagnoses of serious mental illness (e. g., schizophrenia, schizoaffective disorder, bipolar disorder, major depression), and have a BMI > 25, and willing to get a medical clearance letter from a primary care doctor with assistance from the study staff if randomized to the Peer GLB group. Additionally, participants who are randomly assigned to the Peer GLB intervention will have to have been cleared by their primary care physician to participate in light- to-moderate physical activity.

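### Does the thin analysis text leave the 12- and 18-month primary hypothesis without a test?

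*Combined protocol and SAP*

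**What the plan says.** Section 2 (Study Design and Statistical Procedures) sets one primary hypothesis, that a larger share of the Peer GLB arm will reach "clinically significant weight loss (5% weight loss) at 12 and 18 months than UC participants". Assessments "will occur at baseline and at 6, 12, and 18 months post-randomization". The same section places the secondary outcomes at 6, 12 and 18 months, so the 6-month visit belongs to the secondary hypothesis only.

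The analysis text follows the aims in section 2. First: "We will use descriptive and multivariate statistics (e.g., logistic regression, generalized linear mixed effects models) to examine differences in primary and secondary outcomes". Second: "We will also explore interactions between treatment conditions and client- level characteristics", which serves the moderator aim. No significance level, sidedness, visit contrast or rule for combining 12 and 18 months appears there. The rest of the supplied text adds no analysis rule; section 12 only lists interim analysis among the items the DSMB reviews.

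Section 1 points elsewhere for the fuller account: this protocol covers the effectiveness trial, "which is represented by Aims 1-3 outlined in the grant proposal for the current NIMH funded study". That grant is cited as attached but is not among the documents supplied.

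**The concern.** The hypothesis names two visits and the analysis text names none. Because the methods are only examples, a mixed model over all follow-up visits with a single treatment term is not ruled out in words. That term estimates an effect averaged over the visits fitted. It can be significant because of early benefit alone.

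The timing makes this more than a formality. "Peer GLB lasts 12 months and consists of weekly core group sessions", with contact tapering to monthly sessions in the last six months, and the final visit falls six months after the programme ends. Fading is plausible, and 18 months is the test of durability. If the benefit had gone by then, an averaged effect could be reported as support for an 18-month claim that the 18-month data do not bear out, while separate visit tests would say otherwise. If instead a result at either visit were enough, two unadjusted tests would raise a multiplicity question.

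**Working it through.** **No figure to reproduce.** The plan gives arm sizes, "the 12-month Peer GLB intervention (n=150) or 2) to usual care (n=150"), but no power, response rates, significance level or dropout. Everything below except 150 per arm is assumed: complete data, two-sided 0.05, usual care 20% at every visit, Peer GLB 34.3% at 12 months (difference d = 0.143), no difference at 18 months, and correlation r between visit-specific test statistics of 0.5 or 0.76.

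**Standard errors.** SE = sqrt[(p1(1-p1) + p2(1-p2))/150].
- 12 months: sqrt[(0.1600 + 0.2254)/150] = 0.0507. Then 0.143/0.0507 = 2.82, and power = Phi(2.82 - 1.96) = 0.81 (0.80 with the pooled-variance test).
- 18 months: sqrt[(0.1600 + 0.1600)/150] = 0.0462.

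**Effect pooled over 12 and 18 months.** Mean difference = 0.143/2 = 0.0715. SE = (1/2) sqrt[0.0507² + 0.0462² + 2r(0.0507)(0.0462)].
- r = 0.5: SE 0.0420, z = 1.70, chance of significance = Phi(1.70 - 1.96) = 0.40.
- r = 0.76: SE 0.0454, z = 1.57, chance = 0.35.

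**Effect pooled over 6, 12 and 18 months, 6-month effect equal to the 12-month effect.** Mean difference = 2(0.143)/3 = 0.0953.
- r = 0.5: SE 0.0402, z = 2.37, chance = 0.66.
- r = 0.76: SE 0.0451, z = 2.11, chance = 0.56.

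**The same with half the effect at 6 months (27.15%).** Mean difference = 0.0715; SE 0.0397 or 0.0445; chance = 0.44 or 0.36.

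Simulation of the binary outcomes (12,000 trials per setting) agrees:

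| Analysis, benefit gone at 18 months | r about 0.5 | r about 0.76 |
|---|---|---|
| Pooled 12 and 18 months | 0.41 | 0.35 |
| Pooled 6, 12, 18; 6-month effect equal | 0.661 | 0.556 |
| Pooled 6, 12, 18; 6-month effect half | 0.446 | 0.355 |
| Both visits significant | about 0.025 | about 0.025 |

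**Other readings of the hypothesis.** With 80% power at each visit, requiring both gives bivariate-normal power of 0.687 at r = 0.5 and 0.729 at r = 0.8. If either visit were enough at an unadjusted 0.05, the familywise error would be 1 - 0.95² = 9.75% for independent tests, and 9.5% to 8.4% for r from 0.3 to 0.7.

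**Reading the text against these cases.** The three-visit average brings 6 months into the primary test, although section 2 separates it from the primary hypothesis. The two-visit average respects the visits but gives one number where the hypothesis speaks of two. Logistic regression, the first method listed, fitted to the 5% responder outcome at 12 months and again at 18 months, uses the stated outcome and visits and needs nothing the plan lacks. A mixed model with treatment-by-visit terms would supply the same two comparisons. The pooled figures therefore describe an analysis that the plan does not put forward.

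**The case for a change.** The strongest case for acting is that the text really is silent. A primary hypothesis at two visits should come with a named model, two contrasts and a success rule, and stating them would need wording only. The divergence is not small: under another set of assumptions (usual care 15%, Peer GLB 30% at 6 and 12 months, 15% at 18), the three-visit single term was significant in 79-92% of simulated trials, against about 2% when both visits had to succeed.

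The silence stands, and so does the arithmetic. Two parts of the case do not. First, it faults a model that appears nowhere in the plan and, in its three-visit form, cuts across the plan's own split between primary and secondary visits. Second, it treats a both-visits requirement as settled. That is a natural reading, but no decision rule is written, and the secondary hypothesis uses the same construction for several outcomes at three visits, where requiring significance everywhere is an unlikely intent. Writing in a both-visits rule could add a criterion the investigators did not choose, at a cost in power (69-73% where each visit has 80%, for r of 0.5 to 0.8).

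The supplied text is also an ethics-board study description that refers to a grant for these aims. It can show that the detail is absent here, not that the trial lacks it.

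**Conclusion.** The concern does not call for a change. The plan leaves out how the two visit comparisons will be tested and combined, but it fixes the outcome, its direction and the two visits, and it lists a method that tests each of them. An analyst working from the hypothesis would compare the arms at 12 and at 18 months and report both. That is an ordinary gap in a short document, not a wrong analysis.

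The size of the problem under the unfavourable choice is conditional throughout. It is about 35-41% for the pooled two-visit effect, which fits the text better, and 56-66% if an equal 6-month effect is added. These figures assume 20% on usual care, about 80% power at 12 months, complete data and total loss of benefit by 18 months. Partial fading and dropout were not modelled, and other rates and correlations move the figures in either direction. None of those inputs comes from the documents, and the pooled model is not one the plan proposes.

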We will use multiple methods to recruit clients. We will do presentations at staff and client meetings and host lunches/ dinners at the research sites to introduce the project to clients and staff and answer any questions they may have about the project. Interested participants will be asked to provide study staff with their names and contact information. We will also accept provider referrals. Study staff will then initiate contact with interested clients via telephone or in person at each site to further explain the project and set up a face-to-face meeting at the study site to screen potential participants for eligibility, and for those eligible conduct the written consent process.

Once a client has been screened for eligibility into the study and provided informed consent, the study staff will schedule the initial baseline interview based on participants’ availability and preference. The baseline interview will last approximately 90-minutes and will be conducted by a trained research assistant (RA) in a private room at the study site in participants’ preferred language (English or Spanish). Randomization will occur after participants have completed the baseline interview on a 1-to1 ratio to intervention or usual care condition by a computer-generated random number program with treatment assignment kept in sealed, opaque envelopes. For participants randomized to the Peer GLB intervention, study staff will provide each participant a copy of the approval letter that the participant can take to their primary care physician for review and signature. Participants will be required to bring their doctor’s approval letter to the first Peer GLB group meeting in order to participate in the lifestyle intervention. The study staff, with assistance from the peer specialist at each study site, will help coordinate participants’ visits to their primary care physician to obtain this medical clearance. Failure to obtain this approval letter will preclude the individual from participating in the Peer GLB intervention. For participants randomized to the intervention group, baseline interviews will occur at most two weeks before the first group session. After the baseline interview is completed, the study staff will provide the participant the date and time of the first group session meeting.

Peer-Led Group Lifestyle Balance Intervention

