Peer GLB, is based on an established group-based lifestyle intervention adapted from the original Diabetes Prevention Program (DPP) lifestyle program²⁶ by the DPP Lifestyle Resource Core at the

University of Pittsburgh's Diabetes Prevention Support Center (DPSC). Peer GLB is a goal-based behavioral intervention aimed to achieve loss and maintenance of 7% baseline body weight through modest dietary restrictions (e.g. reduce fat intake by <25%) and increase moderate physical activity (e.g., brisk walking) to 150 min/wk.²¹ GLB consists of weekly core group sessions (3 months), bi-monthly (twice a month) transitional group sessions (3 months), and monthly maintenance sessions (6 months.) delivered in community settings (i.e., supportive housing agencies.

Core features of Peer GLB include: integration of safe and appropriate nutritional education, physical activity and behavioral change, strong emphasis on the use of self-monitoring tools (e.g., food and physical activity logs) with regular feedback, and the incorporation of problem solving techniques to address barriers to healthy eating and physical activities. Examples of session topics and themes include: being a fat and calorie detective, healthy eating, move those muscles, problem-solving, four keys to healthy eating out, etc. The intervention includes a group facilitator curriculum manual and DVDs specifying session-by-session instructions, scripts, and group activities (e.g., portion size demonstrations, use of pedometers, problem solving steps) as well as participants' handouts for each session. Intervention materials are available in English and Spanish. Throughout the program, participants are given session handouts, commercially available fat and calorie-counting book, self- monitoring books to tracking food intake and physical activity, pedometers with instructions, program calendar, and a chart to self-monitor their weight twice a week over the course of the program. During session, participants are also shown the intervention DVD's to augment the educational content of the intervention. For English speaking participants, the Peer GLB groups will be delivered in English. For Spanish speaking participants, the Peer GLB groups will be delivered in Spanish.

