In addition to completing these general trainings, which is a prerequisite for being hired, peer specialists at each supportive housing agency will receive training conducted by the study team in the GLB intervention prior to beginning the clinical trial. Peer specialists will complete the intensive 2-day, standardized training in the GLB intervention offered by the DPSC (the developers of the intervention). This training will teach peer specialists how to properly deliver each session of the intervention stepby- step. Additionally, the research staff will also provide training to peer specialists in research fundamentals and collecting anthropometric measures (i.e., weight) and simple physical activity measures (e.g., how many minutes of physical activity participants engaged in weekly) in order to become proficient in standardized measurement consistent with the GLB intervention. As additional training in the intervention prior to the clinical trial, peer specialists will practice delivering weekly GLB sessions and collecting anthropometric and physical activity measures during mock workshops with the study PI and project director. Once the clinical trial begins, peer specialists will receive regular supervision and support from the supervisors at their agency, as well as from research staff. Supervisors from the supportive housing agencies will provide daily oversight and supervision regarding the peer specialists' job responsibilities and delivery of services. The peer specialists will also receive ongoing weekly to biweekly supervision and support from the PI, the project director, and expert consultants in both the delivery of peer services generally, and the GLB intervention specifically, as well as research processes, throughout the trial. These supervision meetings will include review of weekly sessions, discussion and group problem-solving of emerging issues, feedback on fidelity monitoring ratings, and support for the delivery of Peer GLB. Supervision meetings will be conducted via teleconference calls to accommodate everyone's schedules and facilitate communication across all study sites and in person, when necessary. We will also invite the supervisors of the peer specialists at their site to participate in these meetings.

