Lastly, participants assigned to the intervention will be asked to complete one semi-structured qualitative interview that focuses on the participants' experiences with the group facilitator and explores specifically how intervention services were delivered from the participants' perspective. This semi-structured qualitative interview will be conducted after the transition phase of an intervention group has been completed. Participants who attended at least two intervention sessions will be asked to complete the interview and a total of 55 participants are expected to participate. The interviews last approximately 90 minutes and will be conducted in person by Drs. [name] (PI) & [name] (PD) and/or a trained research assistant at the study site. Examples of questions include: Is there anything that makes the healthy lifestyle peer specialist/facilitator unique from other provider staff that you have worked with? What are some of the peer specialist's/facilitator's best qualities? What kinds of things did your peer specialist/facilitator do to model or show you how to engage in a healthy lifestyle?

Criteria for Early Discontinuation

Early discontinuation from the study will be ascertained by the group facilitator in consultation with the participants' service providers (e.g., case managers) at the supportive housing agency. Participants who during the course of the project are in need of detoxification and are at acute risk of suicide or homicide will be referred for treatment and discontinued from the study. Moreover, participants that develop contraindications to participating in a weight loss program, such as receiving active cancer treatment (radiation/chemotherapy), develop liver failure, have a cardiovascular event (e.g., unstable angina, myocardial infarction) and become pregnant or are planning a pregnancy during the study period will be discontinued from the study.

4. Study Drugs or Devices: Not applicable.

5. Study Instruments

Structured Interviews: Baseline and 6, 12, and 18-month Follow-Up

The structured interview includes the collection of basic anthropometric measures and a simple physical activity measure by trained research staff:

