"Thank you for your interest in our study. The purpose of this project is to evaluate a free group-based healthy lifestyle program to help [Agency] clients who are overweight or obese reduce and manage their weight. The goal of this program is help participants improve their eating habits and increase their engagement in physical activities. The study is being conducted through a partnership between [Agency] and the Columbia University School of Social Work. If you are eligible and you choose to participate, you will be randomly assigned to either 1) continue receiving your usual services or 2) to continue receiving your usual services plus participate in a 12-months healthy

lifestyle program that will be held at [site]. Random assignment is like a lottery and means that you have a 50/50 chance of being assigned to either group. If you are not randomly assigned to receive the healthy lifestyle program, you will continue receiving your usual services, but you will not participate in the healthy lifestyle program. If you are randomly assigned to receive the healthy lifestyle program, you will continue receiving your usual services and you will also be asked to attend the healthy lifestyle groups every week for 12 consecutive weeks. After you attend the program for 12 weeks, you will be asked to attend follow-up groups once a month for 9 months. Each group will last approximately 90 minutes and will be facilitated by a trained peer specialist.

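### Only the Peer GLB arm is treated in study groups, yet the analysis text does not require the primary comparison to allow for group; if outcomes correlate within groups, its intervals are too narrow.

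*Combined protocol and SAP*

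**What the plan says.** Section 3 (Study Procedures) sets individual allocation: "Randomization will occur after participants have completed the baseline interview on a 1-to1 ratio to intervention or usual care condition". Section 1 gives 150 clients per arm.

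Treatment in the Peer GLB arm is delivered in groups. Section 2 states: "Peer GLB lasts 12 months and consists of weekly core group sessions", followed by transitional and maintenance phases. The script in Section 7 (Recruitment) adds: "Each group will last approximately 90 minutes and will be facilitated by a trained peer specialist". It also tells clients that those in usual care will not take part in the programme. A group moves through the phases as a unit: Section 3 places a qualitative interview as "conducted after the transition phase of an intervention group has been completed".

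Some randomised Peer GLB clients may never enter a group. On medical clearance, Section 3 says: "Failure to obtain this approval letter will preclude the individual from participating in the Peer GLB intervention".

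The primary hypothesis in Section 2 compares the proportions reaching 5% weight loss at 12 and 18 months. The analysis text at the end of Section 2 offers "statistics (e.g., logistic regression, generalized linear mixed effects models) to examine differences in primary and secondary outcomes". It does not say which model serves the primary outcome, and it names no random effect or cluster variance.

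**The concern.** This is a partially nested design: outcomes in one arm may be correlated within treatment groups, and the other arm has no study groups. Members of a group share a facilitator, group activities and each other's company for a year. A positive correlation is plausible, though the documents do not establish one.

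Two analyses that satisfy the text ignore it: plain logistic regression, and a mixed model whose only random effect is the person. With repeated visits, the second is a natural reading of the mixed-model option. Either would understate the variance of the Peer GLB proportion. The interval for the primary effect would be too narrow, and part of the apparent power would be spurious. The text also gives no rule for Peer GLB clients who belong to no group.

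**Working it through.** **Inputs from the documents.** 150 clients per arm, individual 1:1 allocation, a binary primary outcome, and study groups in the Peer GLB arm only. There is no power calculation to reproduce. Alpha, response rates, group size, number of groups and ICC are not stated.

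**Assumptions.** Two-sided 5% level; responders 28% (Peer GLB) and 15% (usual care); no dropout; usual-care clients independent; ICC 0.02, 0.05 and 0.10. Case A has all 150 Peer GLB clients in 15 groups of 10. Case B has 30% (45 clients) ungrouped and 15 groups of 7.

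**Variance on the log-odds scale, ignoring groups.**
- Peer GLB: 1/(150 × 0.28 × 0.72) = 0.03307
- Usual care: 1/(150 × 0.15 × 0.85) = 0.05229
- Sum: 0.08536

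**Allowing for groups.** Multiply the Peer GLB term by DE = 1 + f(m − 1)ICC, where f is the fraction grouped and m the group size. The variance ratio is (0.03307 × DE + 0.05229)/0.08536. Its square root is the standard error ratio, and 300 divided by it is the equivalent number of clients.

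| Case | ICC | DE | Variance ratio | SE ratio | Equivalent clients |
|---|---|---|---|---|---|
| A | 0.02 | 1.18 | 1.070 | 1.034 | 280 |
| A | 0.05 | 1.45 | 1.174 | 1.084 | 255 |
| A | 0.10 | 1.90 | 1.349 | 1.161 | 222 |
| B | 0.02 | 1.084 | 1.033 | 1.016 | 291 |
| B | 0.05 | 1.21 | 1.081 | 1.040 | 277 |
| B | 0.10 | 1.42 | 1.163 | 1.078 | 258 |

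**Coverage by simulation** (beta-binomial groups, 60,000 runs, nominal 95%), at ICC 0, 0.02, 0.05 and 0.10:
- Case A, unadjusted logistic interval: about 95.3%, 94.7%, 93.3% and 91.0%.
- Case A, unadjusted interval for the difference in proportions: about 95%, 94%, 91.5% and 88%.
- Case A, difference in proportions with a group-based variance in the Peer GLB arm and Satterthwaite degrees of freedom: about 95% throughout.
- Case B, unadjusted logistic interval: about 95.4%, 94.8%, 94.4% and 93.4%.

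**What a mixed-model coefficient estimates.** The marginal log odds ratio is ln(0.28/0.72) − ln(0.15/0.85) = 0.79. In a logistic model with a normal random intercept in the Peer GLB arm only, set to give 28% overall and the stated ICC, the treatment coefficient is 0.73 at ICC 0.05 and 0.67 at ICC 0.10. That coefficient is conditional on group. It is not the comparison of proportions that Section 2 poses.

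**The case against.** The strongest reply is that this is silence rather than error. The analysis text gives examples only, and a generalized linear mixed model can carry a group effect. Section 1 refers to a grant proposal that outlines these aims and is not supplied. This stands as a limit: the point concerns only what the supplied documents require.

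The correlation may also be small. Section 3 says "The intervention includes a group facilitator curriculum manual and DVDs specifying session-by-session instructions, scripts, and group activities", and peer specialists "receive ongoing weekly to biweekly supervision and support from the PI", the project director and consultants. That is a fair reason to expect a low ICC, but not a reason to fix it at zero.

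Three stronger readings are tempting, and the documents do not support them.
- **That the test gives excess false positives for an inert programme.** If Peer GLB affects nobody, individual randomisation keeps the unadjusted test valid. Simulated rejection rates of about 7.5% and 10.3% (groups of 10, ICC 0.05 and 0.10, 20% responders in both arms) arise only when groups truly differ but the average effect is zero.
- **That the logistic analysis loses as much as the difference in proportions does.** On the latter scale the standard error is about 5%, 13% and 25% larger in case A (about 270, 235 and 193 clients). The method the plan names first loses less, as the table shows.
- **That usual care is known to be free of clustering.** Section 14 lists wellness groups among usual services. The contrast holds for study treatment only, and independence in usual care is an assumption.

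**Conclusion.** The point holds. A primary analysis that satisfies the current wording can ignore group, and at any positive within-group correlation its interval is then too narrow. The size is conditional on the assumed response rates, group sizes and ICC. For the logistic model there is no harm at ICC 0, little at 0.02 (coverage about 94.7%), and a modest to material loss from about 0.05 (about 93%, falling to 91% at 0.10) with groups of 10. It is roughly half as large, in standard error terms, if 30% never join a group. This is a change worth making before analysis; it does not show that the trial is invalid or that the investigators will in fact omit group. Confidence is medium, because nothing in the documents fixes the ICC and the grant has not been seen.

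**What to change.** In the analysis text of Section 2, state the following:
- The primary comparison is the marginal difference in the proportions achieving 5% weight loss. Its variance allows for intervention group in the Peer GLB arm only, with a small-sample (Satterthwaite-type) correction.
- If a partially nested logistic mixed model is used, the marginalised difference in proportions is reported, not the conditional coefficient.
- Usual-care clients, and Peer GLB clients who never join a group, stay in their randomised arm as singletons. Independence within usual care is stated as an assumption.
- A person effect is added wherever several visits are modelled.
- Group and facilitator identifiers are recorded, and the ICC is reported.

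The cost is analysis wording and two identifiers in the dataset; the attendance logs and session recordings already planned may supply group membership. Intervals will be wider. In case A, at ICC 0, 0.02, 0.05 and 0.10, power is about 79%, 77%, 76% and 74% for the unadjusted logistic test. It is about 77%, 73%, 67% and 57% for the corrected difference in proportions, and about 74%, 71%, 65% and 56% for the corrected mixed model. At ICC 0 the price is therefore about 2 to 5 points; above that, part of the unadjusted power is spurious. The mixed-model interval is somewhat conservative at ICC 0, covering about 97%.
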